## Sample Size and Data Analysis

**If you uploaded a separate research protocol document in the 'Research Protocol' page, cite the applicable section and page numbers from that document in the answer boxes below.**

**1 \* Provide the rationale and sample size calculations for the proposed target population:**

Our study is based on 88 KCNQ1 Thr224Met probands who were identified as part of another research study and chose to undergo clinical confirmation of their genotype and clinical evaluation for long QT syndrome. We cannot approach probands who chose not to undergo the return of results process. These 88 probands have over 700 first degree family members who may be eligible for cascade screening with our intervention. We can assume some of the family members have died and some may not live in Lancaster County, but a very large proportion will be eligible for testing. Due to privacy laws we cannot approach a family member without permission from the proband. With permission from the proband, we will send family letters or we will provide family letters to probands for them to share with family members. This study will compare the rate of uptake of cascade screening before and after our intervention of a simplified cascade screening program. Given that an individual who undergoes cascade screening before our intervention, during the 'traditional' period does not need to undergo testing again, we cannot statistically compare the difference in the proportion of family members who undergo cascade screening before and after the intervention or the statistical power that our study will have to detect a difference in uptake. That being said, our experience suggests that uptake of cascade screening will be very low among the Amish during the 'traditional' phase when cost, transportation, and an invasive test are barriers. This pilot study will test whether we can overcome these barriers and detect a meaningful improvement in uptake of cascade screening, disclosure to family members, and uptake of appropriate medical intervention. We will define this meaningful improvement a priori as a 15% improvement. For example, if we have 3% of eligible individuals undergo cascade screening during the traditional phase, we would deem 18% of eligible individuals getting tested a clinically meaningful increase. This would translate into 15/500 getting tested before our intervention and 87/485 getting tested after implementing our intervention. Another way of looking at this is that approximately 2-3 probands would initiate cascade screening before the intervention and 12-13 would after the intervention (assuming 7 children per proband).

For the interview portion of the study, participants (adults only) will be sampled purposively to include roughly 30 probands and 45 family members. In order to maximize variability with respect to the genetic test results (e.g., positive and negative), whether or not they shared their results, and primary implementation outcomes (e.g., whether or not they underwent cascade screening), we will enroll 15 probands who shared results with family members, 15 probands who did not share results, 15 family members who underwent cascade screening and were mutation positive, 15 family members who underwent cascade screening and were mutation negative, and 15 family members who did not undergo cascade screening. The goal of this sampling strategy was to achieve maximum variation and minimal informational redundancy. A guide for qualitative research is usually to include approximately 15 interviewees in order to obtain saturation and a homogeneous sample with maximum variation. Therefore, we expect to reach saturation and have a good representation of our participants.

**2 \* Provide the plan for data analysis. Include in the description the types of comparisons that are planned (e.g., comparison of means, comparison of proportions, regressions, analysis of variance, etc.), which is the primary comparison/analysis, and how the analyses proposed will relate to the primary purposes of the study:**

Our primary outcome is the rate of uptake of cascade screening before ('traditional') versus after ('simplified') the intervention. Uptake for this outcome is defined as the proportion of first degree family members (i.e. offspring and siblings) of the initial 88 probands who undergo cascade screening out of all eligible first degree family members (as defined by the Fisher book). We will compare the proportion before versus after the simplified screening approaches. Any individuals who undergo screening before the intervention will no longer be eligible for screening with the simplified cascade screening so the denominator will decrease accordingly. We have chosen to use the denominator of all first degree relatives defined by the Fisher book because this number is not dependent on participants returning the surveys where they will provide information on how many family members they told (and how many they have). Our secondary outcome includes the proportion of informed relatives who get screened. The number of participants screened for all outcomes will be obtained from charts (as [name] is ordering physician for all tests).

Our secondary outcomes are:

- Extent of disclosure of genotype results before and after the intervention. This outcome is defined as the number of family members (siblings and children) told (reported via survey) out of the total number of proband first degree relatives (known from the Fisher Book and asked on the survey).
- Proportion of informed first-degree relatives who get screened before and after the intervention. This outcome is defined as the number of family members tested out of the number told by probands (reported via surveys)
- The overall rate of uptake of preventative therapy among probands and family members (e.g., see a cardiologist and/or take a beta-blockers)

Analyses of secondary outcomes (a) and (b) will occur in the same manner as the primary outcome, by comparing proportions before and after the intervention. For secondary outcome (c), we don't expect the proportion of appropriately treated carriers to be impacted by our intervention, but rather the absolute number of treated individuals would be impacted by detecting more carriers with improved cascade screening. For the disclosure outcome (a), we will compare results using the denominator based on Fisher book data and based on data reported in the survey. For the uptake of screening among those informed outcome (b), the denominator is based on the survey results (the proband will be asked who they disclosed results to and the family member will be asked if their family member told them). For the uptake of clinical recommendation outcome (c), we will use data from the participants' charts to determine whether beta-blocker therapy was indicated and prescribed. We will gather data from the survey on whether participants are following the recommendations. While we don't expect our intervention to change the proportion of individuals appropriately treated, we will compare the proportions before and after the intervention to confirm this assumption.

ID: VIEW4E02806052800  
Name: v2\_Sample Size and Data Analysis

HP-00081981

Sharing of Results\_V2

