## Privacy of Participants

**If the study does not involve interaction with participants, answer "N/A" to the questions below.**

1 \* Describe how you will ensure the privacy of potential participants throughout the study (**privacy refers to persons and their interest in controlling access to themselves**):

Participant interactions will take place in the privacy of the participant's home at a time the participant feels comfortable and agrees to talk. Participants may elect to have a family member or significant other present during research interactions. The participant is in control of who is present and can choose to postpone discussion until a later time if they choose.

2 \* Describe the location where potential participants will receive research information and detail the specific actions the study team will take to ensure adequate privacy areas:

The consent process, survey completion, specimen collection and interviews will be performed in the privacy of the participant's home. Typically these interactions occur in the kitchen or living room. Not uncommonly small children are present when the consent is performed. Interactions in the kitchen or living room is the culturally accepted setting for these types of interactions. It would be inappropriate to use other more private settings in the home, i.e., the bedroom, for these interactions.

3 \* Describe potential environmental stressors that may be associated with the research:

Potential stressors include if some family members wish to participate and others do not. We will endeavor to ensure that no family member feels coerced into participating just because another family member is participating by obtaining individual consent from each participant and stressing that this is strictly voluntary and no one is required to participate.

4 \* Will this study have a site based in the European Union?

Yes  No

5 \* Will the study have planned recruitment or data collection from participants while they are located in the European Union?

Yes  No

**Access link below for information about the EU General Data Protection Regulations to assist in answering these questions.**

<https://www.umaryland.edu/oac/general-data-protection-regulation/>

HP-00081981

Confidentiality of Data\_V2

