### **B. Statistical methods with respect to each outcome**

#### **B1. Aim 1 (cascade screening intervention)**

##### **B1.1 Primary outcome**

Our primary outcome is the rate of uptake of cascade screening before ('traditional') versus after ('simplified') the intervention. Uptake for this outcome is defined as the proportion of first degree family members (i.e. offspring and siblings) of the initial 70 probands who undergo cascade screening out of all eligible first degree family members (as defined by the Fisher book). We will compare the proportion before versus after the simplified screening approaches. Any individuals who undergo screening before the intervention will no longer be eligible for screening with the simplified cascade screening so the

denominator will decrease accordingly. We have chosen to use the denominator of all first degree relatives defined by the Fisher book because this number is not dependent on participants returning the surveys where they will provide information on how many family members they told (and how many they have). Our secondary outcome includes the proportion of informed relatives who get screened. The number of participants screened for all outcomes will be obtained from charts (as [name] is ordering physician for all tests).

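### The before/after difference in uptake can be compared statistically, and the primary result needs a family-clustered interval beside its 15-point benchmark

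*Combined protocol and SAP*

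**What the plan says.** Sample Size and Data Analysis, item 1, and SAP A1 both say "we cannot statistically compare the difference in the proportion of family members who undergo cascade screening before and after the intervention", and that power to detect a difference cannot be given either. The reason offered is that a relative screened in the traditional period has no need of a second test.

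The same text then says "This pilot study will test whether we can overcome these barriers and detect a meaningful improvement in uptake of cascade screening" and "We will define this meaningful improvement a priori as a 15% improvement". Its example moves from 3% to 18%, or 15/500 before and 87/485 after, so the benchmark means 15 percentage points.

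Sample Size and Data Analysis, item 2, defines primary uptake as the "proportion of first degree family members (i.e. offspring and siblings) of the initial 88 probands" who are screened, out of all eligible relatives listed in the Fisher book. SAP B1.1 has the same definition with 70 probands. Relatives screened before the intervention are removed, "so the denominator will decrease accordingly". The stated analysis is: "We will compare the proportion before versus after the simplified screening approaches".

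Neither document names a test, model, interval or significance level, or allows for correlation between relatives of one proband. Yet access is decided family by family: "Due to privacy laws we cannot approach a family member without permission from the proband". Against that, the Privacy of Participants section says undue pressure will be avoided "by obtaining individual consent from each participant", so clustering is probably partial.

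**The concern.** The plan calls a comparison impossible and also promises it. The reason given does not support the first statement. Removing relatives already tested makes the second proportion conditional on being untested, but both proportions and their difference remain estimable.

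Three things are at stake. First, a point estimate set alone against 15 points does not let a reader tell a clear result from a chance one. Second, if an ordinary two-proportion interval were added later, it would be too narrow whenever uptake runs in families. Third, the disclaimer hides the real limits of the comparison: depletion of willing relatives, unequal period length and the second reminder.

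**Working it through.** **Inputs.** From the documents: 15/500 and 87/485 (item 1; SAP A1); 88 probands (protocol) or 70 (SAP). Assumed, because the documents give neither: the intraclass correlation (ICC) of uptake within families, and how far a family's willingness persists from one period to the next. Families are taken as near-equal in size.

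**1. The plan's example.** 0.03 × 500 = 15; 500 − 15 = 485; 0.18 × 485 = 87.3, stated as 87. Uptake is 3.00% and 17.94%, a difference of 14.94 points. At 7 children per proband, 15/7 = 2.1 and 87/7 = 12.4, matching the stated 2-3 and 12-13 probands. The example reproduces.

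**2. Interval for that example.** SE = √(D × [0.03 × 0.97/500 + 0.1794 × 0.8206/485]), with D = 1 + (500/F − 1) × ICC and F the number of families. For F = 70 and ICC 0.3, D = 1 + 6.143 × 0.3 = 2.84 and SE = 1.90 × √2.84 = 3.21 points.

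| ICC | SE, 70 families | 95% CI | SE, 88 families | 95% CI |
|---|---|---|---|---|
| 0 | 1.90 | 11.2 to 18.7 | 1.90 | 11.2 to 18.7 |
| 0.1 | 2.42 | 10.2 to 19.7 | 2.30 | 10.4 to 19.5 |
| 0.3 | 3.21 | 8.7 to 21.2 | 2.95 | 9.2 to 20.7 |
| 1 (bound) | 5.08 | 5.0 to 24.9 | 4.53 | 6.1 to 23.8 |

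The table assumes no persistence. Under full persistence the two periods are positively correlated and the ICC 0.3 interval is 9.9 to 19.9 (70 families) or 10.2 to 19.7 (88). Siblings count as relatives, so probands may share them. If merging left 35 or 20 clusters, the ICC 0.3 interval would be 6.6 to 23.3 or 4.3 to 25.6 (SE 4.25 or 5.45).

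**3. Power against zero, 3% versus 18%.** Power = Φ(0.15/SE − 1.96). It is at least 97% up to ICC 0.5 with 70 or 88 families. At ICC 0.3 it is 94% with 35 clusters and 79% with 20.

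**4. The benchmark alone.** Chance that the observed difference reaches 15 points, for 70 families [88]:

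| True gain | ICC 0 | ICC 0.3, no persistence | ICC 0.3, full persistence |
|---|---|---|---|
| 12 points | 5% | 16% [14%] | 2% [2%] |
| 18 points | 93% | 81% [84%] | 70% [71%] |

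**5. Coverage of 95% intervals.** These are simulations with beta-binomial families, removing relatives tested in period 1; coverage is around each scenario's mean difference. For 3% versus 18%, the naive two-proportion interval covers 88–92% [89–93%] at ICC 0.1 and 75–86% [80–88%] at ICC 0.3, the upper end being full persistence. The family bootstrap covers 93–95% with 70 or 88 families, 93–94% with 35 clusters and 91–93% with 20.

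**6. Depletion.** Suppose each family's uptake probability is the same in both periods, with mean μ. Expected uptake among those still untested is then E[p(1 − p)]/E[1 − p] = μ(1 − ICC). At μ = 10% with no true change, this gives 9% at ICC 0.1 and 7% at ICC 0.3, so differences of −1.0 and −3.0 points. The clustered interval then excludes zero 8% or 30% of the time (8% or 32% with 88 families), nearly always as a decline. Without persistence the figure is 5%. For 3% versus 18%, full persistence lowers the expected gain from 15 to 14.4 (ICC 0.1) or 13.4 (ICC 0.3).

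**The case against.** The plan's caution is partly right. Relatives tested early leave the comparison, so neither a plain independent-samples test nor a paired test fits. The study is a pilot with a descriptive benchmark, and its own example excludes zero even at ICC 1. The 14.94 against 15 is rounding of a count. All of this stands, and it limits the harm to unstated precision. It does not support the claim that no comparison or power statement is possible.

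A stronger objection is that the clustered interval does not solve everything. Its coverage of about 94% is around the scenario mean, which already contains the depletion bias. Under full persistence at ICC 0.3 with 70 families, it covers the true 15-point gain only about 87% of the time. If merging probands who share relatives left 20 very unequal clusters, coverage fell to about 84–88% in assumed examples. Both points stand as caveats. A naive interval shares the depletion bias and ignores clustering as well, and no interval conveys no precision at all.

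Two further points stand. The plan's conversion of tests into whole families at 7 children per proband implies an ICC near 1, so the wide end of the range should not be dismissed. An interval over periods of different length may also look more rigorous than it is: the simplified period lasts about 9 months and the traditional period has no stated length. The choice of bootstrap over a cluster-robust variance is a matter of preference.

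**Conclusion.** The concern holds. The statement in both documents is wrong as written and conflicts with the plan to test, detect and compare in the same documents. The difference can be estimated and powered with the family as the unit.

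The cost of leaving it is a primary result without precision. In the plan's own example the 95% half-width is about 3.7 points if relatives are independent ((18.7 − 11.2)/2) and about 6.2 points at ICC 0.3 with 70 families ((21.2 − 8.7)/2). These sizes rest on assumed ICC and persistence and on near-equal families. The finding that a comparison is possible rests on none of them. This should be fixed, but it does not invalidate a pilot. The interval would describe chance only.

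**What to change.** 1. In Sample Size and Data Analysis, item 1, and SAP A1, replace the clause denying a statistical comparison and power with: *uptake in each period is measured among relatives untested at the start of that period.*
2. In item 2 and SAP B1.1, add: *The primary estimate is the risk difference (after minus before) among eligible first-degree relatives untested at the start of each period, with a two-sided 95% confidence interval from a bootstrap that resamples whole families across both periods. Probands who share relatives form one cluster, and a shared relative is counted once. The number and sizes of clusters will be reported.*
3. Keep the a priori benchmark, write it as 15 percentage points, and report the interval beside it. Do not replace it with a rule that the interval excludes zero.
4. Add: *The interval reflects chance only. It does not remove confounding from unequal period length or the second reminder. Removing relatives already tested leaves a less willing group, which biases the difference downward when family willingness persists.*
5. If power or precision is quoted, first reconcile 88 with 70 probands and count the merged clusters, then show a range over ICC.

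The cost is wording in both documents and a few lines of code. No new data are needed: tests come from charts, denominators from the Fisher book, and SAP B1.3 foresees few gaps in the primary outcome. The price is a wider interval than the naive one. Its lower limit falls below 15 points in the plan's own example even at ICC 0 (11.2), and coverage weakens if few or very unequal clusters remain.

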## Sharing of Results

1 \* Describe whether results (study results or individual subject results, such as results of investigational diagnostic tests, genetic tests, or incidental findings) will be shared with subjects or others (e.g., the subject's primary care physicians) and if so, describe how it will be shared:

The KCNQ1 genetic testing is a clinical test and will be performed in the CLIA/CAP certified laboratory at the Clinic for Special Children. Results will be provided to participants by the genetic counselor at the Clinic for Special Children. The counselor will provide information regarding appropriate medical follow-up, treatment, and recommended testing of first-degree relatives.

An electrocardiogram will be offered to family members found to carry the risk allele. A copy of the ECG will be provided to participants.

Samples will be stored for possible future genetic analysis. These analyses are for research purposes only and results will not be shared with participants, placed in their medical records or shared with their physicians.

ID: V1EW4E02808CBD800  
Name: v2\_Sharing of Results

HP-00081981

Behavioral Methods and Procedures\_V2

## Psychological/Behavioral/Educational Methods & Procedures

You indicated on the "Type of Research" page that your study involves a psychological/behavioral/educational method or procedure such as a survey, questionnaire, interview, or focus group.

1 \* Select all behavioral methods and procedures which apply to this study:

- Surveys/questionnaires
- Key informant or semi-structured individual interviews
- Focus groups or semi-structured group discussions
- Audio or video recording/photographing
- Educational tests or normal educational practices (education instructional strategies, techniques, curricula, or classroom management methods)
- Individual or group behavioral observations
- Psychosocial or behavioral interventions
- Neuropsychological or psychophysiological testing
- Deception
- Other psychosocial or behavioral procedures

ID: VIEW4E09416F57800

Name: v2\_Psychological/Behavioral/Educational Methods and Procedures

HP-00081981

Surveys/Questionnaires\_V2

## Surveys/Questionnaires

You indicated that this study involves surveys and/or questionnaires.

If you uploaded a separate research protocol document in the 'Research Protocol' page, cite the applicable section and page numbers from that document in the answer boxes below.

1 \* List all questionnaires/surveys to be used in the study, including both standardized and non-standardized assessments:

Baseline Proband questionnaire  
 Post-intervention Proband questionnaire  
 Post-intervention mutation negative Family Member questionnaire  
 Post-intervention mutation positive Family Member questionnaire  
 Family Member declined testing questionnaire  
 Medical, social, and family history questionnaire  
 Medication form

2 \* Upload a copy of all questionnaires/surveys:

Name	Created	Modified Date
 Family positive(0.03)	11/8/2018 1:53 PM	5/16/2022 11:33 AM
 Family negative(0.03)	11/8/2018 1:51 PM	5/16/2022 11:33 AM
 Family no testing(0.02)	2/3/2019 7:31 PM	5/16/2022 11:33 AM
 Medication Flow Sheet.docm(0.01)	2/4/2019 12:18 PM	2/4/2019 12:18 PM
 Medical, Social, and Family history form(0.01)	2/4/2019 12:17 PM	2/4/2019 12:17 PM
 Proband baseline(0.03)	9/13/2018 4:06 PM	2/3/2019 7:28 PM
 Proband followup(0.02)	11/8/2018 1:48 PM	2/3/2019 7:27 PM

3 \* What is the total length of time that each survey is expected to take?

20 minutes

4 \* Are any of the questions likely to cause discomfort in participants or cause harm if their confidentiality were breached? (i.e., Illegal activities)

Yes  No

5 \* Do any questions elicit information related to the potential for harm to self or others?

Yes  No

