In the invitation letter, family members will be asked to take part in a study involving screening for the KCNQ1 variant, including any or all of the following: provide a saliva sample to check for the KCNQ1 genetic variant at no cost to them, complete a questionnaire about their attitudes and experience with genetic testing, and possibly take part in an in-person interview. They will be instructed to return a response form or call the Amish Research clinic if they are interested in participating in the study.

Family members who indicate, by returning the response card or by phone call, that they are interested in participating in the free genetic testing will be visited in their home by a study team member and an Amish liaison. Initial interactions are described in the Recruitment Section. For those who are interested in participating, informed consent will be obtained from adults and parents of minor children. Written assent will be obtained from minors aged 13-17; verbal assent will be obtained from children 7-12 years of age. Consent and assent will be obtained prior to any study procedures are performed. The informed consent process is detailed in the Consent Section of this application. Participants/parents will be asked to complete a questionnaire including demographics, medical and family history, and medications (uploaded in.

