### Sample Collection and Processing:

A saliva sample will be collected from each participant. DNA will be used for clinical testing for the KCNQ1 Thr224Met variant and an aliquot will be stored for possible future genetic analyses. Saliva samples will be collected from adults and children who are able to provide sufficient saliva volume for testing. For small children and infants, mouth swabs will be used to collect saliva.

Participants should not eat, drink, smoke or chew gum for one hour prior to collection of saliva. For saliva, participants will be asked to expectorate approximately 2 mL of saliva in an Oragene DNA (DNA Genotek, Ontario, Canada) saliva collection kit. For small children and infants, a swab will be used to collect saliva. The swab will be placed in oral cavity and sample will be collected from the right and left side of the cheek by rotating the swab 10 times in up and down motion on each side. The swab will be placed in collection container. All samples will be stored at ambient temperature until transport to the receiving laboratory.

Clinical genetic test results will be returned to the participant by a genetic counselor [MOD 6: and/or study team member. Individuals who are tested for the risk allele (positive or negative) will also be offered an electrocardiogram (ECG) along with information regarding appropriate medical follow-up, recommendations for treatment, and recommended testing of first-degree relatives.] along with information regarding appropriate medical follow-up, recommendations for treatment, and recommended testing of first-degree relatives. After they have received their KCNQ1 results, participants who agreed to take part in the survey portion will be mailed a questionnaire about their attitudes and experience with genetic testing. If the family member only agrees to completing a survey (not the KCNQ1 testing), a family information / consent letter (uploaded to Surveys Section) in the Additional documents Section) and a questionnaire will be mailed with instructions for completion and return.

Probands who indicate that they want genetic testing for their minor children who live at home will be contacted to set up an appointment for testing as described above. Minor children will not complete the survey or interview portions of the study.

Stamped and addressed envelopes will be provided for all return mailings.

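### Outcomes (b) and (c): relatives' survey reports are listed only after the intervention, and pooling relatives with probands lets the before/after proportion in (c) move through case mix alone

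*Combined protocol and SAP*

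**What the plan says.** The application's Surveys/Questionnaires page (item 1) lists seven instruments. Probands have a pair: the "Baseline Proband questionnaire" and a post-intervention form. Under Justification, Objective, & Research Design (item 2), the first of these covers sharing of results, health behaviour and impact since the results were returned. Relatives' experience forms are the "Post-intervention mutation negative Family Member questionnaire", the "Post-intervention mutation positive Family Member questionnaire" and the "Family Member declined testing questionnaire". Sample Collection and Processing gives the timing for tested relatives: "After they have received their KCNQ1 results, participants who agreed to take part in the survey portion will be mailed a questionnaire".

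The remaining two instruments are a history questionnaire and a medication form. Study Procedures describes their use at the home visit, after consent and ahead of sampling: "Participants/parents will be asked to complete a questionnaire including demographics, medical and family history, and medications".

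SAP B1.2, repeated in the application's Sample Size and Data Analysis (item 2), sets out the two outcomes:

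- **Outcome (b)** is relatives tested divided by relatives told by probands. For its survey-based denominator the text adds: "the proband will be asked who they disclosed results to and the family member will be asked if their family member told them". The number tested comes from charts for every outcome.
- **Outcome (c)** is uptake of preventive care among probands and family members together. Charts show whether a beta-blocker was indicated and prescribed. For the rest: "We will gather data from the survey on whether participants are following the recommendations". The investigators expect no change in the proportion and will compare it before and after to confirm this.

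Neither text says how the two sources in (b) are combined, to which period a relative's report belongs, or whether (c) is split by type of participant.

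**The concern.** Both comparisons can change their data source or case mix at the moment the intervention starts.

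In (b), a second source of who was told becomes available only post-intervention. If it is added to the after denominator alone, that denominator grows for a reason unrelated to behaviour, and uptake among the informed looks lower.

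In (c), the carriers known before are nearly all probands, who have already been through clinical evaluation. Those known after include many newly found relatives. A pooled proportion then mixes any real change in care with the change in who is counted. The comparison exists to confirm that nothing changed, so a shift caused by case mix alone would defeat its purpose, and a real change could be masked in the same way.

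**Working it through.** **The plan's own figures.** SAP A1 gives 15/500 before and 87/485 after. Check: 0.03 × 500 = 15; 500 − 15 = 485; 0.18 × 485 = 87.3, given as 87. These belong to the primary outcome. No figure is given for (b) or (c), so the rest is illustration.

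**Outcome (c): who is in the pool.** Inputs:

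- Relatives tested: 15 before, and 15 + 87 = 102 cumulatively after (SAP A1).
- Carrier risk in first-degree relatives: 50% (application, Justification, item 3).
- Probands: 88 (application) or 70 (SAP). Both are used as a range.

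Relative carriers known: 15 × 0.5 = 7.5 before; 102 × 0.5 = 51 after.

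| Probands | Relatives' share before | Relatives' share after |
|---|---|---|
| 88 | 7.5/95.5 = 7.9% | 51/139 = 36.7% |
| 70 | 7.5/77.5 = 9.7% | 51/121 = 42.1% |

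**Outcome (c): effect on the pooled rate.** Pooled rate = (probands × proband rate + relative carriers × relative rate) / total. The treatment rates are assumptions and are held the same in both periods, so the true change is zero. Relatives' data are taken as complete in both periods.

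| Probands treated / relatives treated | 88 probands: before → after | 70 probands: before → after |
|---|---|---|
| 50% / 50% | 50.0% → 50.0% | 50.0% → 50.0% |
| 50% / 30% | 46.25/95.5 = 48.4% → 59.3/139 = 42.7% | 37.25/77.5 = 48.1% → 50.3/121 = 41.6% |
| 50% / 10% | 46.9% → 35.3% | 46.1% → 33.1% |
| 30% / 50% | 31.6% → 37.3% | 31.9% → 38.4% |

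The direction depends on which group has the higher rate. If relatives' data were also missing before, the second row would start at 50.0%. The fall would then be 7.3 points with 88 probands or 8.4 with 70, instead of 5.8 or 6.5. Most of the shift is therefore case mix rather than the missing survey.

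**Outcome (b): effect on the denominator.** Suppose proband surveys capture 60% of true disclosures. That figure is an assumption, borrowed from the survey return rate expected in SAP B1.3. Suppose relatives' forms independently capture a share r. Combined capture = 1 − (1 − 0.6)(1 − r), to be compared with 0.6 for probands alone.

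| r | Combined capture | Denominator ratio | Apparent uptake multiplied by |
|---|---|---|---|
| 0 | 0.60 | 1.00 | 1.00 |
| 0.2 | 0.68 | 1.13 | 0.88 |
| 0.4 | 0.76 | 1.27 | 0.79 |
| 0.6 | 0.84 | 1.40 | 0.71 |

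This applies only if the sources are merged and relatives' reports count only in the after period. With proband reports in both periods the multiplier is 1.00.

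**The case against.** A reader might infer that relatives have no baseline form at all and that all before data come from probands. The documents do not support this. Relatives who agree to testing complete history and medication forms at enrolment, which could show existing beta-blocker use. Charts supply the numerator of (b) and the indication and prescription parts of (c), and can cover relatives tested in the traditional period. What stands against this is limited: the enrolment forms are not described as covering disclosure or cardiology visits, and they miss relatives who decline testing.

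A reader might also infer a bias of known size in (b). The formal definition rests on telling by probands, who are surveyed in both periods, so (b) can be computed symmetrically. Asking relatives as well could be meant as a cross-check. The family forms are not reproduced and may ask about the earlier period. All of this is fair, and it means that no fixed figure can be attached to (b). What remains is that the text leaves the denominator open.

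On (c), a baseline survey of relatives would not cure the problem, because a newly found carrier has no earlier carrier status. Relatives also could not be approached without the proband's permission or contact. The plan itself says that the number treated is what should change. These points are right, and they argue for splitting the analysis rather than for a new survey. They do not rescue the pooled comparison, which the plan still intends to make.

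Finally, these are secondary outcomes of a pilot with no stated test or error rate. That limits the consequence. It does not make the comparison interpretable.

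**Conclusion.** The point holds for the survey-based part of (b) and for the pooled proportion in (c).

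For (b), the plan leaves open a denominator that could be wider after than before. Any bias from this runs against the intervention. Its size is unknown, and it is zero if only proband reports are used.

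For (c), at the plan's example counts and 50% carrier risk, the relatives' share of known carriers rises from about 8% to 37% (88 probands) or from 10% to 42% (70). Any difference in treatment rate between the groups then moves the pooled figure: 48.4% to 42.7% with 88 probands at assumed rates of 50% and 30%, and not at all at equal rates. The composition figures rest on the plan's hypothetical testing counts; the treatment rates are assumptions only.

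The primary outcome, which uses charts and the Fisher Book, is unaffected.

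**What to change.** In SAP B1.2 and the matching text of Sample Size and Data Analysis (item 2):

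1. For (b), make the proband-reported denominator the main analysis in both periods, and show the combined proband and relative source as a sensitivity analysis. State how the sources are merged and how each report is assigned to a period.
2. For (c), compare before and after within probands. Report relatives separately, together with the absolute number treated, which is the quantity the plan expects to change.
3. If the family forms do not already ask, and data collection still allows, add items on when the relative was told and when care began.

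Items 1 and 2 change analysis text only and need no new data. Item 3 needs a few questions on forms already mailed and an IRB modification. The drawbacks are small before numbers for relatives (about 7 or 8 carriers in the plan's example) and recall error in any dates collected. Proband reports also remain incomplete at about 60% return, so the main analysis of (b) uses the same source in both periods but is not a full count.
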